## **PASI75 and PASI90 response**

PASI75 response and PASI90 at Week 16 will be evaluated for those subjects in whom the assessment occurred due to sufficient skin involvement (at least 3% BSA affected with psoriasis) (which is planned to be a subset of the FAS). These binary variables will be evaluated in the same fashion as ACR response, i.e. a logistic regression model with treatment and randomization strata as factors and weight as a covariate.

The primary estimand of PASI 75 and 90 response is the odds-ratio (each secukinumab dose vs. placebo) at week 16 in the FAS population that would be observed if all patients dropping out or being unblinded before week 16 or having with missing PASI data at week 16 were non-responders.

## **Changes in DAS28-CRP**

Between-treatment differences in the change from baseline in DAS28-CRP will be compared by means of a MMRM with treatment regimen, analysis visit, and TNF-alpha inhibitor status as factors, and weight and BSL as continuous covariates. Treatment by analysis visit and BSL by analysis visit will be included as interaction terms in the model. An unstructured covariance structure will be assumed for this model. The significance of the treatment effects for secukinumab regimens at different analysis visits will be determined from the pairwise comparisons performed between secukinumab regimens and placebo at the appropriate analysis visits.

The primary estimand for DAS28-CRP is the estimated treatment differences (each secukinumab dose vs. placebo) at week 16 in the FAS population applying the MMRM model described above under the MAR assumption for any missing data.

### **2.6.3 Handling of missing values/censoring/discontinuations**

#### **Missing data**

Missing data for binary efficacy variables for data up to Week 52 will be handled as follows:

- Subjects who drop out of the trial for any reason will be considered non-responders from the time they drop out through Week 52 for active groups or through Week 24 for placebo group.
- Subjects who do not have the required data at baseline and at the specific time point to compute response will be classified as non-responders.

Continuous variables (e.g. ACR20 components) will be analyzed using a mixed-effects repeated measures model (MMRM) which is valid under the missing at random (MAR) assumption. As such, single-point imputation of missing data will not be performed (e.g. LOCF). For analyses of these parameters, if all post-baseline values are missing then these missing values will not be imputed and this subject will be removed from the analysis of the corresponding variable, i.e. it might be that the number of subjects providing data to an analysis is smaller than the number of subjects in the FAS.

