**Document History – Changes compared to previous final version of SAP**

Date	Reason for update	Outcome for update	Section and title impacted (Current)
08-Aug-2017	Clarifying the analyses for between AIN457 comparisons	Amendment 03	2.6.3, 2.7.3
	Aligning terminology with protocol by replacing “no disease progression” with “no structural progression”		2.6.1, 2.7.1, 4.2.8
	Correct description of the planned “de facto”-type analyses		2.6.2.2
			[REDACTED]
			[REDACTED]
			[REDACTED]
	Correct typographical errors Update references		Throughout document 5
			[REDACTED]

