### **Comparative efficacy data**

Comparative efficacy analyses (i.e. inferential efficacy comparisons with placebo) will focus on the time period when both active drug and the placebo are given in a manner suitable for making comparisons (e.g. double-blind). For AIN457F2342 this is the first 16/24-weeks of treatment depending on the endpoint considered. Comparative efficacy will be performed based on the FAS population using the randomized treatment. After week 24, the active secukinumab regimens will be compared using confidence intervals on the FAS population using treatment sequence.

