## **Efficacy data following treatment switch**

Data will also be presented after Week 24, by a combination of the ‘original’ and ‘switch’ treatment groups and will be referred to as treatment sequence. These treatment sequences represent the treatment combinations the subjects experience over the course of the entire trial in case of treatment switch (e.g., placebo patients who are reassigned to 150 or 300 mg secukinumab at Week 16 (rescued) or Week 24).

All listings will be presented by treatment sequence.

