### **2.2.2 Treatment groups**

The summaries by treatment will be performed by the randomized treatment or treatment sequence. For some safety summaries (e.g. exposure-adjusted) the ‘switch’ treatment may be summarized separately.

- Randomized treatment:
  - AIN457 150 mg No Load
  - AIN457 150 mg
  - AIN457 300 mg
  - Placebo
- Treatment sequence:
  - AIN457 150 mg No Load
    - Stay with 150 mg
    - Up-titrated to 300 mg
  - AIN457 150 mg
    - Stay with 150 mg
    - Up-titrated to 300 mg
  - AIN457 300 mg
  - Placebo Non-responder – AIN457 150 mg
    - Stay with 150 mg
    - Up-titrated to 300 mg
  - Placebo Non-responder – AIN457 300 mg
  - Placebo Responder – AIN457 150 mg
    - Stay with 150 mg
    - Up-titrated to 300 mg
  - Placebo Responder – AIN457 300 mg

*Note:* up-titration subgroup analysis will be performed for the final Week 112 DBL only.

Up-titrated subgroup will include those subjects who are up-titrated to AIN457 300 mg in the second year. Additional sequences could be reported such as Any AIN457; Any AIN457 150 mg; Any AIN457 300 mg if applicable.

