## **Rescued patients**

[figure not shown]
In general if not stated otherwise (as e.g. for vdH-mTSS), the handling of data for subjects who are **rescued at Week 16** will be handled in the following fashion for comparison with placebo at Week 20 and Week 24:

[figure not shown]
For each binary endpoint, a subject will be considered as a non-responder at Week 20/24 for that endpoint if the subject is a non-responder (including missing imputed non-responder) at Week 16. If a subject is a responder at Week 16 for that endpoint, the actual value at Week 20/24 will be used (missing is considered as non-responder). This will be done for all treatment regimens in order to minimize bias.

[figure not shown]
- For continuous endpoints, the goal of the analyses would be to estimate what would have happened if the patients had stayed on the original treatment. Thus, the data collected after a Placebo patient switches to secukinumab will be treated as missing for the placebo group and will be analyzed using a mixed-effects repeated measures model (MMRM) which is valid under the missing at random (MAR) assumption. For secukinumab patients that are rescued, the actual values will be used in the analysis.

[figure not shown]
Data collected **after Week 24** will generally be presented as ‘observed case’; i.e. all available data for each time point will be included in the analyses. In addition, multiple imputation will be used for long-term (e.g. after week 52) comparison for selected endpoints.

For comparisons between the active arms the rescue penalty will not be applied as the effect of rescuing is the same for both treatment groups (i.e. the patient continues to receive secukinumab 150 mg or 300 mg every 4 weeks).

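### SAP 2.6.3 counts later dropouts as binary non-responders to Week 52 in the randomised secukinumab arms, but only to Week 24 in subjects who started on placebo and switched to secukinumab

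*SAP*

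**What the plan says.** SAP 2.6.3 opens its missing-data rules with one lead-in: "Missing data for binary efficacy variables for data up to Week 52 will be handled as follows". Two bullets follow.

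- Bullet 1 covers subjects who leave the trial. They are "considered non-responders from the time they drop out through Week 52 for active groups or through Week 24 for placebo group".
- Bullet 2 covers absent data: "Subjects who do not have the required data at baseline and at the specific time point to compute response will be classified as non-responders". It has no limit by group or by reason.

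Later in 2.6.3, under rescued patients, the SAP says that data after Week 24 are generally presented as observed case, so that "all available data for each time point will be included in the analyses".

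After Week 24 the unit of reporting is the treatment sequence. SAP 2.1 explains: "These treatment sequences represent the treatment combinations the subjects experience over the course of the entire trial in case of treatment switch". SAP 2.2.2 adds that "The summaries by treatment will be performed by the randomized treatment or treatment sequence", and lists the placebo-origin sequences separately, by Week 16 response and by the secukinumab dose that follows. SAP 2.1 also states: "After week 24, the active secukinumab regimens will be compared using confidence intervals on the FAS population using treatment sequence".

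Protocol 9.4.3 confines its corresponding bullets to data up to Week 24 and makes observed case the general rule afterwards, without distinguishing groups.

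**The concern.** From Week 24 every subject still on treatment receives secukinumab, and results are shown by sequence. Bullet 1 nevertheless sets the end of non-responder imputation by randomised origin. If it is applied as printed, a subject randomised to secukinumab who leaves at Week 30 is a failure at Week 52. A placebo subject who switched and also leaves at Week 30 is simply not counted.

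The same underlying outcomes would then give a higher reported rate in the switch sequences. SAP 2.13 plans a Week 52 analysis for regulatory submission or publication, so these rates are likely to be read side by side. Two programmers could also follow 2.6.3 in good faith and produce different denominators, because no visible sentence ranks bullet 1, bullet 2 and the observed-case default.

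**Working it through.** **Reading the rules together.** Take binary response at Week 52 for a subject who left at Week 30.

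| Rule in SAP 2.6.3 | Randomised to secukinumab | Randomised to placebo, switched at Week 16 or 24 |
|---|---|---|
| Bullet 1 (dropouts) | Non-responder | Imputation ended at Week 24 |
| Bullet 2, read literally | Non-responder | Non-responder |
| General default after Week 24 | Observed case: not counted | Observed case: not counted |

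For the randomised secukinumab arms, bullet 1 is the specific rule and reasonably overrides a default that applies only generally. For the switched subjects, bullet 1 gives no instruction after Week 24, so either bullet 2 or the default decides. There are two ways to reconcile the text:

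1. Bullet 2 covers only subjects still in the trial. The bullets then agree, but switched dropouts are not counted while those in the randomised secukinumab arms are failures. A switched subject who misses only the Week 52 visit is a failure, yet one who left at Week 30 is not.
2. Switched subjects count as active groups. Both the conflict and the inequality then disappear.

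The visible SAP states neither. The sentence on multiple imputation for long-term comparisons does not settle it: it gives the period after Week 52 as its example and names no endpoints.

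**Size.** The documents give no Week 52 rate, no post-switch dropout rate and no figure that depends on this rule, so there is nothing to reproduce. The assumptions are a rate of 51% (the ACR20 planning rate for secukinumab in protocol 9.7, borrowed for illustration) and a missing fraction d of 5%, 10% or 15% after the switch. The 25% first-year dropout in protocol section 4 includes losses before the switch, so it is not a post-switch rate.

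- If 51% is the imputed rate, observed case = 0.51/(1 − d).
- If 51% is the rate among subjects with data, imputed = 0.51 × (1 − d).

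| d | Observed case when imputed = 51% | Gap (points) | Imputed when observed = 51% | Gap (points) |
|---|---|---|---|---|
| 5% | 53.7% | 2.7 | 48.45% | 2.55 |
| 10% | 56.7% | 5.7 | 45.9% | 5.1 |
| 15% | 60.0% | 9.0 | 43.35% | 7.65 |

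The range is about 2.6 to 9 points. It is zero if bullet 2 governs or if switched subjects count as active.

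**Scale.** Protocol 5.2 puts 165 subjects in each placebo arm. The Amendment 1 rationale expects about 66% of placebo subjects to be Week 16 non-responders. Before any loss ahead of the switch, that gives 165 × 0.66 ≈ 109 in each placebo non-responder sequence and 165 × 0.34 ≈ 56 in each placebo responder sequence. Ten percent missing is about 11 and 6 subjects.

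The 95% half-width of a 51% rate is 1.96 × √(0.51 × 0.49/n): 9.4 points at n = 109 and 13.1 points at n = 56. The largest gap, 9.0 points, exceeds neither.

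**The case against.** A reader might infer that the two bullets are opposite rules and that 2.6.3 contradicts itself. The documents do not support so strong a claim. The same pair of bullets appears in protocol 9.4.3 and SAP 2.5.3. In the protocol, the second bullet explains required data as the joint counts and enough ACR components, which suggests incomplete assessments rather than departures. If bullet 2 also covered dropouts, bullet 1 and its Week 24 and Week 52 limits would do nothing. That argument stands against calling it a contradiction. It does not remove the unequal handling, because it leaves bullet 1 in sole charge of dropouts.

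A second defence is that Week 24 merely marks where the placebo group ends, since nobody stays on placebo after that visit. Switched subjects would then be active. This is a fair reading and would dispose of the point, but the SAP does not say it, and 2.2.2 keeps these subjects in placebo-origin sequences.

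Third, all endpoints listed in SAP 2.6.1 are at Week 16 or 24, and section 2.7 is redacted. The document history records one change to both 2.6.3 and 2.7.3, described as "Clarifying the analyses for between AIN457 comparisons". A governing rule may sit in 2.7.3, and this limits confidence. Still, the lead-in in 2.6.3 itself reaches Week 52, so its own wording should be clear.

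Fourth, observed case in the switch sequences agrees with protocol 9.4.3. That is true, but the protocol applies observed case to every group after Week 24. The inequality comes from the SAP extending imputation to Week 52 for the active groups alone.

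**Conclusion.** The point holds as a minor one, with medium confidence. As printed, SAP 2.6.3 allows Week 28 to 52 binary response rates to rest on non-responder imputation in the randomised secukinumab arms and on observed case in the placebo-switch sequences. That would favour the switch sequences by method alone. The size above rests on the assumed rate and missing fractions, and the shift stays within the sampling uncertainty of one sequence. It would, however, be systematic and is avoidable.

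A reader might go further and infer that the confirmatory results or the secukinumab dose comparisons are biased. The documents do not support that. H1 to H27 are tested at Week 16 or 24, so they and alpha control are untouched. The three randomised secukinumab arms share one rule and remain comparable with each other. The switch sequences already differ from those arms in treatment start and are split by Week 16 response, so any comparison with them is descriptive. The conclusion is also conditional on the redacted 2.7.3.

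**What to change.** In SAP 2.6.3, state one missing-data rule for binary endpoints from Week 28 to Week 52. It should apply alike to the randomised secukinumab arms and, from the switch onward, to the placebo-switch sequences. The simplest choice is the non-responder imputation already written for the active groups. Keep the Week 24 limit only for placebo subjects who left before receiving secukinumab, and report them outside the switch-sequence denominators.

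Say that this rule takes precedence over the general observed-case sentence up to Week 52. Show observed-case results as supportive, with the number observed per sequence and visit, and document the difference from protocol 9.4.3. Check 2.7.3 for consistency.

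The cost is SAP wording and one denominator rule in programming. Reported rates in the switch sequences would be somewhat lower than under observed case, and a departure from the protocol that already exists for the active groups becomes wider. Treatment, visits and the Week 16 and 24 tests do not change.

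Using observed case for all sequences after Week 24 would also restore equal handling and would match the protocol, but it would reverse what bullet 1 now says for the active groups.

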## **Premature unblinding**

Patients who were unblinded prior to the scheduled timepoint will be considered non-responders from the time of unblinding up to the end of the placebo-controlled period (Week 24).

## **Rescued patients**

[figure not shown]
In general if not stated otherwise (as e.g. for vdH-mTSS), the handling of data for subjects who are **rescued at Week 16** will be handled in the following fashion for comparison with placebo at Week 20 and Week 24:

[figure not shown]
For each binary endpoint, a subject will be considered as a non-responder at Week 20/24 for that endpoint if the subject is a non-responder (including missing imputed non-responder) at Week 16. If a subject is a responder at Week 16 for that endpoint, the actual value at Week 20/24 will be used (missing is considered as non-responder). This will be done for all treatment regimens in order to minimize bias.

[figure not shown]
- For continuous endpoints, the goal of the analyses would be to estimate what would have happened if the patients had stayed on the original treatment. Thus, the data collected after a Placebo patient switches to secukinumab will be treated as missing for the placebo group and will be analyzed using a mixed-effects repeated measures model (MMRM) which is valid under the missing at random (MAR) assumption. For secukinumab patients that are rescued, the actual values will be used in the analysis.

[figure not shown]
Data collected **after Week 24** will generally be presented as ‘observed case’; i.e. all available data for each time point will be included in the analyses. In addition, multiple imputation will be used for long-term (e.g. after week 52) comparison for selected endpoints.

For comparisons between the active arms the rescue penalty will not be applied as the effect of rescuing is the same for both treatment groups (i.e. the patient continues to receive secukinumab 150 mg or 300 mg every 4 weeks).

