3.6 Risks and benefits

Secukinumab has shown either preliminary or confirmed efficacy in several inflammatory diseases. The safety profile of secukinumab is primarily based on the aggregate safety data from 10 large completed phase II/III psoriasis trials. The evaluation of safety data from completed PsA trials did not show additional safety concerns.

Secukinumab was generally safe and well-tolerated. The most frequently reported adverse events (AE) are infections, especially upper respiratory tract with secukinumab relative to placebo. There was an increase in mucosal or cutaneous candidiasis with secukinumab compared to placebo, but the cases were generally mild or moderate in severity, non-serious, and responsive to standard treatment.

There was a small increase in mild neutropenia cases with secukinumab compared to placebo. Common Toxicity Criteria (CTC) AE grade 3 neutropenia ($<1.0-0.5 \times 10^9/L$) was uncommonly observed with secukinumab, most were transient and reversible without a temporal relationship to serious infections.

Hypersensitivity reactions include urticarial and rare event of anaphylactic reaction to secukinumab were also observed in clinical studies.

Taking into account the individual risks as outlined above, the expected risk profile of secukinumab from a mechanism of action perspective is anticipated to be similar or improved compared to the approved inflammatory cytokine-targeting therapies. The risk to subjects in this trial will be minimized by compliance with the eligibility criteria, close clinical monitoring and extensive guidance to the investigators, provided in the current version of the IB.

From the standpoint of the overall risk-benefit assessment, current trial with secukinumab is justified.

4 Population

The study population will be comprised of the subjects who have passed screening assessments and comply with eligibility criteria.

Subjects can be re-screened only once and no re-screening study related procedures should be performed prior to written re-consent by the subject. Mis-randomized subjects will not be re-screened.

This is an international study and it is expected that approximately 990 subjects will be randomized.

A screening failure rate of 20% and post-randomization dropout rate of 25% is anticipated in the first year. Enrollment will stop as soon as the target number and proportions of randomized subjects in the respective treatment group is reached.

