5.5.9 Discontinuation of study treatment

Subjects may voluntarily discontinue from the study for any reason at any time. They may be considered discontinued if they state an intention to withdraw, fail to return for visits, or become lost to follow-up for any other reason.

If premature discontinuation occurs for any reason, the investigator must make every effort to determine the primary reason for a subject's premature discontinuation from the study and record this information on the appropriate Study Phase Completion eCRF.

Study treatment must be discontinued if the investigator determines that continuation of study treatment would result in a significant safety risk for a subject.

The following circumstances **require** study treatment discontinuation:

- Withdrawal of informed consent
- Subject's request to terminate treatment
- Emergence of the following AEs:
 - Any severe or serious AE that is not compatible with administration of study medication, including AEs that require treatment with an unacceptable co-medication
 - Onset of lymphoproliferative disease or any malignancy except for treated basal cell carcinoma, treated actinic keratoses, treated in situ carcinoma of the cervix or non-invasive malignant colon polyps which are being or have been removed
 - Life-threatening infection
 - Severe hypersensitivity reaction or anaphylactic reaction
- Any laboratory abnormalities that in the judgment of the investigator are clinically significant and are deemed to place the subject at a safety risk for continuation in the study (A general guidance on clinically notable laboratory values is provided in [Appendix 8](#)).
- Pregnancy
- Use of any biologic immunomodulating agent except secukinumab
- Any protocol deviation that results in a significant risk to the subject's safety.

In addition to these requirements for study treatment discontinuation, the investigator should discontinue study treatment for a given subject if there is a lack of improvement or worsening

of their symptoms, or if on balance, he/she thinks that continuation would be detrimental to the subject's well-being. The investigator should discontinue from study treatment subjects who have <20% improvement from BSL in either TJC or SJC at both Week 40 and Week 44.

For subjects who discontinue study treatment, a Dosage Administration Record eCRF should be completed, giving the date and primary reason for stopping study treatment.

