9.4.3 Handling of missing values/censoring/discontinuations

Missing data for ACR20 response and other binary efficacy variables (e.g. ACR50, ACR70, HAQ-DI[®] response, etc.) for data up to Week 24 will be handled as follows:

- Subjects who drop out of the trial for any reason will be considered non-responders from the time they drop out through Week 24.
- Subjects who do not have the required data to compute ACR response (i.e. tender and swollen joint counts and at least three of the five ACR core set variables) at BSL and at the specific time point will be classified as non-responders.

Continuous variables (e.g. ACR components, DAS, etc.) will be analyzed using a mixed-effects repeated measures model (MMRM) which is valid under the missing at random (MAR) assumption. For analyses of these parameters, if all post-BSL values are missing then these missing values will not be imputed and this subject will be removed from the analysis of the

[figure not shown]
corresponding variable, i.e. it might be that the number of subjects providing data to an analysis is smaller than the number of subjects in the FAS.

Data collected after Week 24 will generally be presented as 'observed case'; i.e. all available data for each time point will be included in the analyses.

In general, the handling of data for subjects who are rescued at Week 16 will be handled in the following fashion for comparisons with placebo at Week 20 and Week 24:

- For each binary endpoint, a subject will be considered as a non-responder at Week 20/24 for that endpoint if the subject is a non-responder (including missing imputed non-responder) at Week 16. If a subject is a responder at Week 16, the actual value at Week 20/24 will be used (missing is considered as non-responder). This will be done for all treatment regimens in order to minimize bias.
- For continuous endpoints, the goal of the analyses would be to estimate what would have happened if the subjects had stayed on the original treatment. Thus, the data collected after the subject switches to secukinumab will be treated as missing for placebo subjects and will be analyzed using a MMRM which is valid under the missing at random (MAR) assumption. For secukinumab subjects, the actual values will be used in the analysis.

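### After Week 52 the default observed-case rule drops subjects stopped for joint non-response at Weeks 40 and 44, so the descriptive two-year ACR response rates are biased upward

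*SAP*

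**What the plan says.** **First-year rule for binary endpoints.** SAP 2.6.3 (Missing data) has dropouts "considered non-responders from the time they drop out through Week 52 for active groups or through Week 24 for placebo group".

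**Later data.** Under Rescued patients in the same section, data after Week 24 are generally observed case: "all available data for each time point will be included in the analyses. In addition, multiple imputation will be used for long-term" comparison of selected endpoints, with the time after Week 52 given as the example. Protocol 9.4.3 has the same default ("Data collected after Week 24 will generally be presented as" observed case) and mentions no imputation for this period.

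**Imputation specification.** SAP 4.2.3 describes multiple imputation under missing at random, by treatment group, for visits as far as the primary time point, with Week 16 or 24 as examples. The code shown ends at Week 24.

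**Stopping rule.** Protocol 5.5.9 says the investigator should stop study treatment in "subjects who have <20% improvement from BSL in either TJC or SJC at both Week 40 and Week 44". A subject who stops has an End of Study visit four weeks after the last dose and a follow-up visit twelve weeks after it. In Table 6-2 the first later visit with joint counts is Week 60, and the follow-up visit has none.

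**Loss and use.** Protocol Section 4 states that a "post-randomization dropout rate of 25% is anticipated in the first year". SAP 2.1 compares the active regimens after Week 24 by confidence intervals on the FAS, by treatment sequence.

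**The concern.** ACR20 needs at least 20% improvement in both joint counts (Protocol 6.4.1). Anyone stopped under the Week 40/44 rule is therefore an ACR20 non-responder at both visits, and so also an ACR50 and ACR70 non-responder. The plan counts these subjects as failures through Week 52. From Week 60, under the default, it does not count them at all. Their absence is selection on the outcome being reported.

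Efficacy up to two years is part of the trial's title and stated purpose, so these rates will be read. Three things are at stake:

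- A rate can rise between Week 52 and Week 60 with no change in any subject.
- Dose escalation is allowed from Week 52, so such a rise could be mistaken for a benefit of escalation.
- The arm that loses more non-responders gains most, which distorts the confidence-interval comparisons of regimens. Those comparisons are described as being on the FAS, but observed-case denominators are smaller than the FAS.

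**Working it through.** **Inputs from the documents.** 220 subjects per secukinumab group and 330 on placebo; ACR20 rates of 51% and 15%; ACR50 rate of 35% on secukinumab; two-sided alpha of 1.67% (Protocol 9.7). First-year dropout is 25% (Protocol Section 4).

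**Assumptions.** The 51% planning rate is carried into year 2 as an illustration, because the documents state no Week 104 rate. The 25% is applied to each arm. Year-2 loss and the number stopped under the Week 40/44 rule are not given, so both are varied.

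**Step 1: the plan's own figure.** Fisher's exact power for 51% of 220 against 15% of 330 at alpha 1.67% comes out above 99.99%, in agreement with the stated value of over 99%. The inputs are being read as intended. The contested quantity has no stated figure to reproduce.

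**Step 2: the change of rule alone.** Let R be the rate with dropouts as non-responders and d the proportion lost. The same responders over the observed denominator give R/(1 − d).

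- Responders: 0.51 × 220 = 112.2, about 112. Observed: 220 × 0.75 = 165.
- 0.51/0.75 = 68.0% (about 112 of 165), a rise of 17.0 points.
- Loss of 5%, 10%, 15% or 35% gives 53.7%, 56.7%, 60.0% or 78.5%.
- ACR50 at 25% loss: 0.35/0.75 = 46.7%.

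**Step 3: excess over the full-FAS rate.** If dropouts would have responded at rate q and the full-FAS rate is R, observed case shows (R − d·q)/(1 − d). With R = 51% and d = 25%:

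| q | Observed-case rate | Excess (points) |
|---|---|---|
| 0% | 68.0% | 17.0 |
| 10% | 64.7% | 13.7 |
| 20% | 61.3% | 10.3 |
| 30% | 58.0% | 7.0 |
| 51% | 51.0% | 0 |

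**Step 4: the Week 40/44 rule alone.** Here q = 0 on the last observed joint counts. If the rule removed 3%, 5% or 10% of an arm (assumed), 51% would read 0.51/0.97 = 52.6%, 0.51/0.95 = 53.7% or 0.51/0.90 = 56.7%.

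**Step 5: unequal loss.** Two arms with the same 51% rate but 15% and 25% loss (illustrative) would show 60.0% and 68.0%, an 8-point difference that comes only from the denominator.

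**Step 6: timing.** For the placebo-origin sequences non-responder scoring ends at Week 24, so their dropouts can leave the denominator from Week 28. For the active groups SAP 2.6.3 gives two rules for Weeks 24 to 52: non-responder under Missing data, observed case under Rescued patients. The step falls after Week 52 only if the first prevails; otherwise it comes earlier.

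**The case against.** **Multiple imputation is planned.** A reader might infer that year 2 rests on observed cases only. It does not: the SAP adds multiple imputation in the sentence after the observed-case rule, with after Week 52 as its example. Subjects stopped under the Week 40/44 rule have observed poor joint counts, and a model using that history would keep them in the denominator. This stands as far as it goes. However, the imputation is a supplement for selected endpoints, and the specification that can be read ends before Week 40.

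**Redaction.** SAP entries between 2.6.3 and 2.8 are blacked out, and the document history shows that Section 2.7.3 was amended together with 2.6.3. The selected endpoints, or a longer imputation model, may be set out there. Not seeing them is therefore no fault of the plan.

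**ACR only.** A reader might extend the argument to PASI and HAQ-DI response. Poor joint response does not define failure on skin or function, so for those endpoints selection is possible but not built in.

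**Seventeen points is a ceiling.** A reader might take it as the bias. It requires every dropout, for whatever reason, to be a non-responder, and scoring dropouts that way is itself a conservative convention. If dropouts would have responded as often as those who stayed, the excess is zero. That is implausible for subjects stopped for non-response but possible for other losses.

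**No confirmatory consequence.** None of H1 to H27 concerns a time after Week 24, so type I error and power are untouched. This is correct and limits the weight of the point.

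**Conclusion.** The point holds for ACR20/50/70 under the default presentation. From Week 60 the observed-case rates in the active groups exclude subjects whose last relevant joint counts made them non-responders, and the direction of that bias is upward. Its size is not fixed by the documents. At 25% loss and a 51% rate it is between 0 and 17 points over the full-FAS rate. The part due to the Week 40/44 rule is about 2 to 6 points if that rule removes 3% to 10% of an arm, which is an assumption. The 5.5.9 wording is a direction to investigators, so the number actually stopped could be small.

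The step from 51% to 68% is exact arithmetic for the change of scoring rule at 25% loss; it does not measure how wrong the later rate is. The effect is confined to descriptive two-year rates and confidence-interval comparisons between regimens. It merits correction because the remedy is cheap and the imputation text that can be read does not supply it.

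**What to change.** In SAP 2.6.3:

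1. For ACR20/50/70 after Week 52 through Week 104, count subjects who stopped for lack of efficacy or under the Week 40/44 rule as non-responders, with all FAS subjects of the arm as denominator.
2. For other dropouts, and for PASI and HAQ-DI response, use multiple imputation whose model includes the visits after Week 24, or score them as non-responders. State which, and extend SAP 4.2.3 to match.
3. Show the observed-case rate beside this result, with its n at each visit.
4. Reconcile the two rules for Weeks 24 to 52, and state the rule for the placebo-origin sequences after Week 24.

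No treatment or stopping rule changes. The cost is a short SAP edit, the added imputation programming if that option is chosen, and one extra table per endpoint. The long-term response rates will look less favourable.
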